## **Project summary**

The purpose of this project is to investigate the effects of caffeine chewing gum on the cognitive functions and special operations capabilities of special forces. Using a randomisation crossover design, 20-40 active-duty special forces members who had undergone leave and special forces reserve training were divided into a caffeine trial (CAF) and a placebo trail (PL). After chewing caffeine-containing gum containing 5 mg/kg (CAF group) or caffeine-free gum (PL group) for 15 minutes, we performed a simple reaction test, a stroop test, a visual search test, a grip strength test, a vertical jump test, a 20-metre sprint test, and a counter-terrorism simulation test. A heart rate monitor was used to measure the heart rate and heart rate variability of the participants. Saliva samples were collected and analysed for  $\alpha$ -Amylase, cortisol and caffeine concentrations before the test, after a 15-minute break from chewing gum and at the end of the test. Completion time of cognitive functions, grip strength, vertical jump height, 20 m sprint time, time to completion of the counterterrorism simulation test, and target score will be analysed using paired-sample t-tests.

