#### Experimental procedure

The participants' diets were recorded 3 days prior to the first formal trial and they were asked to repeat the same diet before the next trial. On the day of the experiment, the same breakfast will be served to ensure that the energy intake of the participants is the same.

All experiments were scheduled to start at 8 am. Upon arrival at the assembly site, participants rested in a sitting position for at least 10 minutes. The saliva of the participants was then collected for subsequent biochemical analysis. At the same time. Participants wore a heart rate monitor to record their heart rate and heart rate variability during the experiment. Immediately thereafter, participants chewed either caffeine-containing chewing gum (CAF trail) containing 5 mg/kg or caffeine-free placebo gum (PL trial) for 10 minutes while warming up. After chewing, participants spat out the gum and rested quietly for 15 minutes to collect saliva samples again. Afterwards, a simple reaction test, a stroop test, and a visual search test were performed. At the end of the test, grip strength, reverse action jump and 20-metre sprint were performed under full armour (20 kg load). At the end of the test, the participant was tested on anti-terrorist operations with a Colt 9mm submachine gun. Completion times and target scores were recorded for subsequent analysis. Upon completion of the test, the participant collects another saliva sample to complete the test. The saliva samples are expected to be analysed for  $\alpha$ -Amylase, cortisol and caffeine concentrations.

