## Statistical analysis

All data are presented as averages  $\pm$  standard deviations. The Shapiro–Wilk test was used to examine the normality of the data. The result of were analyzed through a paired sample t test. All data were calculated using SPSS (version 20, Chicago, IL, USA), and the significance level was  $\alpha < 0.05$ .

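### Does the protocol waste the pre-gum saliva sample by comparing amylase and cortisol with a paired t-test alone?

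*Protocol*

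**What the plan says.** Each session has three saliva samples. Under Experimental procedure the first follows at least 10 minutes of seated rest ("The saliva of the participants was then collected for subsequent biochemical analysis"), and the gum comes directly after it. For the second, "participants spat out the gum and rested quietly for 15 minutes to collect saliva samples again". The third closes the session: "Upon completion of the test, the participant collects another saliva sample to complete the test". The Project summary gives the same three times, for amylase, "cortisol and caffeine concentrations before the test, after a 15-minute break from chewing gum and at the end of the test".

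On analysis, the Project summary lists cognitive test times, grip, jump, sprint, "time to completion of the counterterrorism simulation test, and target score will be analysed using paired-sample t-tests". Amylase, cortisol and salivary caffeine are not in that list. Experimental procedure says only "The saliva samples are expected to be analysed for" the three analytes. Statistical analysis says "All data are presented as averages" with standard deviations, uses Shapiro–Wilk for normality, and names the paired t-test in a sentence whose subject is missing, so the outcomes it covers cannot be read from it.

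**The concern.** The first sample is a proper within-session baseline, since it is taken before the gum is given. The only comparative test named is a paired t-test, which by itself does not accommodate three times under two conditions. If it were run on one post-gum sample, CAF against PL, the pre-gum value would appear only in a descriptive table.

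That could cost precision. If a participant's CAF-minus-PL difference before the gum predicts the difference after it, adjusting for the former narrows the interval for the latter at no extra sampling cost. With recruitment of 20 to 40, a two-sided 5% paired t-test has 80% power only for standardised differences of about 0.66 (n = 20) or 0.45 (n = 40), so precision is worth having. At stake would be the width of the interval for two supporting markers, not bias.

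**Working it through.** **1. Does the protocol fix the analysis complained of?** The concern needs a commitment to a paired t-test of post-gum amylase and cortisol without use of the pre-gum value. Three places could contain it.

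- Project summary: assigns the paired t-test to a closed list of performance and cognitive outcomes, with no salivary analyte.
- Experimental procedure: says what is assayed, not how it is compared.
- Statistical analysis: names the test but not the outcomes. If saliva is covered, the test could be applied to a post-gum value or to the change from the pre-gum value. The second use gives the baseline a comparative role.

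None of them makes the commitment.

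**2. Would a post-gum paired t-test be wrong?** No. With randomised order, the pre-gum difference between sessions has expectation zero, apart from period or carryover effects, so leaving it out does not bias the treatment comparison. In simulation under no effect (40,000 replicates per cell), the post-gum paired t-test, the change-score t-test and the baseline-adjusted regression all rejected in 4.7% to 5.2% of trials.

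**3. How much precision could be gained?** The protocol gives no SD, correlation or effect size, so every input here is assumed apart from n = 20 and n = 40. Let r be the correlation between the pre-gum and post-gum CAF-minus-PL differences, with equal variances, balanced sequences and a standardised effect of 0.5. The alternative regresses the post-gum difference on the pre-gum difference and sequence.

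Variance relative to the post-gum paired t-test:

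- change score: 2 − 2r
- baseline-adjusted: (1 − r²) × (1 + 1/(n − 4)), where the second factor is the cost of estimating the slope

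At n = 20 the factor is 1 + 1/16 = 1.0625. At n = 40 it is 1 + 1/36 = 1.028.

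| r | n = 20: formula | n = 20: simulated variance | n = 20: adjusted power | n = 40: simulated variance | n = 40: adjusted power |
|---|---|---|---|---|---|
| 0 | 1.06 | 1.06 | 54% | 1.03 | 86% |
| 0.3 | 0.91 × 1.0625 = 0.97 | 0.96 | 57% | 0.94 | 89% |
| 0.5 | 0.75 × 1.0625 = 0.80 | 0.80 | 66% | 0.76 | 94% |
| 0.7 | 0.51 × 1.0625 = 0.54 | 0.54 | 82% | 0.53 | 99% |

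The post-gum paired t-test has about 57% power at n = 20 and 87% at n = 40. Break-even in variance is where r² = 1 − 1/1.0625 = 0.059, so r ≈ 0.24 at n = 20. At n = 40, r² = 1 − 1/1.028 = 0.027, so r ≈ 0.16. Below these values adjustment costs a little.

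The change-score t-test has 32%, 43%, 57% and 78% power at n = 20 for the same four values of r. It is worse than ignoring the baseline until r reaches 0.5, where 2 − 2r = 1.

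**4. Is a large r to be expected?** Let r1 be the pre/post correlation within a session and r2 the correlation between sessions. Then r = (r1 − r2)/(1 − r2), or r1 = r2 + r(1 − r2). With r2 = 0.5 assumed:

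- r = 0.5 needs r1 = 0.5 + 0.5 × 0.5 = 0.75
- r = 0.7 needs r1 = 0.5 + 0.7 × 0.5 = 0.85

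The session controls may hold r down. "All experiments were scheduled to start at 8 am", diet is repeated, breakfast is the same and participants sit at rest before the first sample. All of this removes session-to-session variation that a baseline would otherwise capture. The third sample also follows the loaded physical tests and the armed simulation, and the protocol gives no correlation for it. The documents do not settle the size, or even the sign, of the gain.

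**The case for a change.** The strongest reply is that Statistical analysis does commit to a test, so this is a matter of what the protocol fixes and not merely of what it omits. One paired t-test does not say whether it applies to a post-gum value, to a change or at each time. The choice matters: at n = 20 and r = 0.3, a change-score test has 43% power against about 57% for a post-gum test. Leaving it open lets the choice be made after the data are seen. The trade also looks lopsided: about 3 points of power lost at r = 0, against 9 gained at r = 0.5 and 25 at r = 0.7.

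Part of this stands. No salivary comparison is specified here, and it should be fixed somewhere before the data are seen. But the SAP is not at hand, and the contrast and covariates for supporting markers are ordinary SAP content. The openness argument also works against the concern: if the reader cannot tell how the t-test will be applied, the protocol has not chosen to discard the baseline.

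The lopsided trade depends on r being moderate or high, which nothing in the protocol supports. Nor is the adjusted analysis foolproof. If sequence is coded +1/−1 and then mean-centred with unequal sequence groups, the intercept becomes the treatment difference plus the period effect times the mean code. With 12 and 8 participants, for example, the mean code is (12 − 8)/20 = 0.2. The protocol does not promise equal groups.

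**Conclusion.** The concern does not hold. The sampling schedule is as described, and the paired t-test is the only comparative test named, but no passage assigns amylase or cortisol to a post-gum comparison that ignores the baseline. What is left is missing detail that a protocol may leave to the SAP, together with a preference between valid analyses.

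No validity is at stake. The possible effect on power at n = 20 runs from a loss of about 3 points to a gain of about 25, and at n = 40 from a loss of about 1 to a gain of about 12 (99% against 87%). These figures assume a standardised effect of 0.5, equal variances, balanced sequences and r between 0 and 0.7. They bear on two supporting markers only; the stated purpose, cognition and special-operations capability, is unaffected. A SAP that assigned these markers to an unadjusted post-gum test would still be defensible, though the choice would then be open to comment on precision.

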## Introduction

Caffeine supplementation has been shown in many studies to increase explosive power, anaerobic capacity, concentration, and reduce muscle soreness and reaction time, and the caffeine mechanism during exercise can be effective in improving endurancerelated performance(1, 2). However, some studies have found that caffeine supplementation is also effective in improving performance in shorter exercise sessions. The mechanism may involve the metabolite of caffeine, methylxanthine, which improves the rate of glycolysis into glucose, making more glucose available to the body. On the other hand, some sports do not allow for timely caffeine supplementation during exercise, so whether the use of caffeinated chewing gum has the same performanceenhancing effect deserves further study.

For members of special forces, the use of caffeine in the form of caffeinated beverages or capsules may result in an increase in the frequency of urination due to overhydration, which may make it difficult to adjust to the demands of the mission. Therefore, the administration of caffeine in the form of caffeinated chewing gum may be one of the solutions to overhydration. Therefore, the purpose of this study was to investigate the effects of caffeine gum on the cognitive functions and special operations capabilities of special operations personnel.

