#### Protocol

#### Pre tests

Prior to the formal test, the participant will undergo at least two anti-terrorist combat simulations to familiarise him/herself with the process of the formal test. The timer will start when the participant passes through the entrance on the first floor. The test will simulate the daily counter-terrorism duties of special forces personnel, conducting space searches and clearing out enemies. Ten targets are placed in the space to be attacked. When the participant finishes clearing the enemies on the first floor, he/she will enter the ground floor to continue searching and clearing the enemies in the space and return to the entrance of the first floor as soon as possible when he/she touches the simulated hostages. Each enemy will be scored using a 10-point target paper. The task completion time and the total score of the target shooting will be used to calculate the intraclass correlation coefficient (ICC) and test-retest reliability for this SAR task. The second simulation test is the cognitive function test, which consists of a simple reaction test, a stroop test and a visual search test. Each participant was given at least 2-3 sessions to familiarise him/herself with the cognitive function tests.

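### No primary outcome among six to eight t-tested outcomes: without adjustment, a 17–34% chance of at least one false difference if caffeine has no effect (two-sided tests, assumed correlation 0–0.7)

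*Protocol*

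**What the plan says.** The Introduction gives the aim in two broad parts and ranks neither: "the purpose of this study was to investigate the effects of caffeine gum on the cognitive functions and special operations capabilities".

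The Project summary gives the list of outcomes to be tested. It opens with "Completion time of cognitive functions, grip strength, vertical jump height, 20 m sprint time" and closes with "time to completion of the counterterrorism simulation test, and target score will be analysed using paired-sample t-tests". That makes six items.

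The first item is not a single measurement. The Pre tests section describes the cognitive function test as one "which consists of a simple reaction test, a stroop test and a visual search test". Nothing says whether the three are combined into one time or tested one by one. The count is therefore six if combined and eight if separate.

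The Statistical analysis section adds one threshold for everything: "All data were calculated using SPSS (version 20, Chicago, IL, USA), and the significance level was" 0.05. It does not say whether tests are one-sided or two-sided. No section calls any outcome primary, main or secondary.

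**The concern.** The outcome on which a trial's conclusion rests is part of its design and belongs in the protocol. How that outcome is analysed, and how the others are adjusted for multiplicity, can sit in a statistical analysis plan. No such plan is at hand, and the point here is not that an adjustment is missing.

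The point is that the protocol fixes the aim, the outcomes, the test and the threshold, but not which result decides. With six to eight candidates, whichever reaches significance can be presented as the answer once the data are known. The simulation exercise alone yields two results, time and shooting score, with no rule for when they disagree. The 0.05 level then describes each test in isolation and not the error rate of the main claim.

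**Working it through.** The protocol states no overall error rate, so there is no figure to reproduce.

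**Inputs from the protocol**
- Number of tests k: 6 as listed (Project summary), or 8 with the three cognitive tests separate (Pre tests).
- Level per test: 0.05 (Statistical analysis).
- Test: paired t-test, n = 20 to 40 (Participants), so 19 to 39 degrees of freedom.

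**Assumptions not in the protocol**
- Two-sided tests.
- Correlation rho between the outcomes' paired differences: 0 to 0.7, equal for all pairs.
- No adjustment elsewhere.
- No effect on any outcome, except where stated.

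**Step 1: independent tests.** The chance of at least one false difference is 1 − (1 − 0.05)^k.
- k = 6: 1 − 0.95^6 = 26.5%
- k = 8: 1 − 0.95^8 = 33.7%

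A two-sided 0.05 test gives a false result in caffeine's favour with probability 0.025.
- k = 6: 1 − 0.975^6 = 14.1%
- k = 8: 1 − 0.975^8 = 18.3%

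**Step 2: correlated tests.** Each participant's difference on outcome j was simulated as √rho × (a shared normal term) + √(1 − rho) × (an outcome-specific normal term). All k paired t-tests were then applied. There were 100,000 replicates per cell; the ranges cover n = 20 and n = 40.

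| rho | k = 6, either direction | k = 6, favouring caffeine | k = 8, either direction | k = 8, favouring caffeine |
|---|---|---|---|---|
| 0 | 26.4–26.5% | 14.0–14.1% | 33.5–33.8% | 18.2–18.4% |
| 0.3 | 24.2–24.4% | 12.1–12.3% | 30.1–30.2% | 15.2% |
| 0.5 | 21.0–21.3% | 10.4–10.7% | 25.5–25.7% | 12.8–12.9% |
| 0.7 | 16.7–17.0% | 8.3–8.4% | 19.4–19.8% | 9.7–9.8% |

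**Step 3: cross-check.** The large-sample normal version is 1 − ∫ φ(u) [Φ((1.96 − √rho·u)/√(1 − rho)) − Φ((−1.96 − √rho·u)/√(1 − rho))]^k du. At rho 0.3, 0.5 and 0.7 it gives 24.1%, 20.7% and 16.4% for k = 6, and 30.0%, 25.0% and 19.1% for k = 8. The agreement is close; the slightly lower values come from replacing t by normal.

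**Step 4: other scenarios**
- Half of the effects real (3 of 6, or 4 of 8): a false difference among the rest has probability 11.1–18.7% in either direction and 5.5–9.7% in caffeine's favour. At independence the first is 1 − 0.95^3 = 14.3% or 1 − 0.95^4 = 18.5%.
- One-sided tests at 0.05: the chance of at least one false result in caffeine's favour is 15–34%.

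**Step 5: behaviour of the fix.** With the primary tested at 0.05, and Holm on the others only if it is significant, the simulated chance of any false positive is 4.9–5.1% when there is no effect anywhere. It is 3.3–4.9% when the primary effect is real and all secondary effects are null.

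**Step 6: cost to secondary tests.** From the noncentral t with noncentrality (effect × √n), the effect detectable with 80% power, in SDs of the difference, is:

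| Level | n = 20 | n = 40 |
|---|---|---|
| 0.05 | 0.660 | 0.454 |
| 0.05/5 (first Holm step, five secondaries) | 0.838 | 0.565 |
| 0.05/7 (first Holm step, seven secondaries) | 0.874 | 0.586 |

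**The case against.** **An analysis plan might already control the error.** Bonferroni over all listed outcomes would bring the overall rate to 4.9% at correlation 0 and 3.1–3.3% at 0.7, with no primary named. This is a fair limit on the percentages, which are conditional on no adjustment elsewhere. It does not supply the missing choice: an adjusted set of six to eight equal outcomes still does not say which one answers the question.

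**The study may be exploratory.** The aim is only to investigate effects, there is no success criterion, and reporting each measure at its own level is a recognised practice. But the protocol never calls itself exploratory, and it sets a significance threshold. If exploratory is what is meant, it should say so and drop confirmatory claims, which the fix allows.

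**The headline range assumes caffeine does nothing, whereas the Introduction expects effects.** That is why the half-real range is given beside it. The upper end, 34%, also needs eight uncorrelated outcomes; with the six items as listed the range is 17–26%.

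**The sentence on the t-test in the Statistical analysis section has lost its object.** The count of outcomes therefore rests on the Project summary alone. That stands as a caveat, but the summary's list is explicit. It leaves out the heart rate and saliva measures, so testing those as well would raise the rates.

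**Conclusion.** The concern holds. No outcome is designated as primary, and six to eight outcomes share one 0.05 level. If nothing is adjusted elsewhere, caffeine has no effect and tests are two-sided, the chance of at least one false difference is about 17% (six tests, correlation 0.7) to 34% (eight independent tests). That is more than three times the nominal 5% even at the low end. The correlation range is assumed, because the protocol gives none. The design is not invalidated, but its main conclusion has no pre-specified basis. This should be corrected, and the correction is cheap.

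**What to change.** Before unblinding, add to the protocol:

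1. One primary outcome, chosen by the sponsor, tested at two-sided 0.05, with the main conclusion based on it alone.
2. A statement of whether the cognitive outcome is one combined measure or three.
3. A statement that all other listed outcomes are secondary (including target score, if simulation time is the primary) and that no secondary result can replace or rescue the primary.
4. One of two rules for the secondaries: test them with Holm only if the primary is significant, which keeps the overall rate at 5%; or report them as estimates with 95% confidence intervals and make no confirmatory claim.

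The cost is two or three sentences and a commitment to one outcome in advance. The primary test loses no power. Under the gated rule, no secondary claim is possible if the primary is not significant. The effect detectable with 80% power at the first Holm step also rises from 0.66 to 0.84–0.87 SD at n = 20 and from 0.45 to 0.57–0.59 SD at n = 40. If that price is too high for a study of this size with a two-part aim, the estimates-only rule avoids it.

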## Introduction

Caffeine supplementation has been shown in many studies to increase explosive power, anaerobic capacity, concentration, and reduce muscle soreness and reaction time, and the caffeine mechanism during exercise can be effective in improving endurancerelated performance(1, 2). However, some studies have found that caffeine supplementation is also effective in improving performance in shorter exercise sessions. The mechanism may involve the metabolite of caffeine, methylxanthine, which improves the rate of glycolysis into glucose, making more glucose available to the body. On the other hand, some sports do not allow for timely caffeine supplementation during exercise, so whether the use of caffeinated chewing gum has the same performanceenhancing effect deserves further study.

For members of special forces, the use of caffeine in the form of caffeinated beverages or capsules may result in an increase in the frequency of urination due to overhydration, which may make it difficult to adjust to the demands of the mission. Therefore, the administration of caffeine in the form of caffeinated chewing gum may be one of the solutions to overhydration. Therefore, the purpose of this study was to investigate the effects of caffeine gum on the cognitive functions and special operations capabilities of special operations personnel.

#### Methods

#### Design

This study used a randomization crossover design with a double-blind experiment, divided into a caffeine trial (CAF) and a placebo trail (PL). After the first trial, participants rested for 7-10 days to recover and then proceeded to the next trial, which was expected to be completed within 1 month. During the trial period, all participants maintained their normal training status and there was no change in the training menu.

## Participants

This study is expected to recruit 20-40 active duty special operations personnel who have received professional counter-terrorism and counter-detection training. Military Police Special Forces and is expected to be conducted by the experimenter after a recruitment seminar with the participants. Before the study, the experimenter will be informed of any problems that may be encountered during the experiment, and the procedure will be fully explained. However, due to the confidentiality of the information provided by the special forces, all names and personal information will be withheld, so the information will be provided in the form of an instruction manual. This study received approval from the Institutional Review Board of Jen-Ai Hospital - Dali Branch (202400036B0). This study was conducted following the Declaration of Helsinki.

